7.9. Sample Size

The PG of 80% has been established for the primary safety endpoint, based on a one-sided 97.5% exact binomial test. The 30-day MAE rate is anticipated to be approximately 9%. Under these assumptions, the required sample size to achieve a level of 90% power is 110 subjects (**Table 4**). Assuming 10% attrition over 30 days, initial enrollment of 121 subjects is necessary.

A PG of 76% has been established for the primary effectiveness endpoint. Anticipating an actual technical success rate of approximately 86%, and based upon a one-sided 97.5% exact binomial test, the required sample size to achieve a level of 90% power is 165 target lesions. Assuming a 1.5 ratio of subjects to treated target lesions, approximately 110 subjects will be necessary (**Table 5**). Since the primary effectiveness endpoint is determined at the time of the index procedure, no attrition has been taken into account.

ⁱ The TALON publication reported the results in 1258 target lesions, among which 132 required preliminary balloon dilatation to deliver the device and technical success ($\leq 50\%$ residual stenosis after atherectomy) was not achieved in 54 lesions. Technical success was calculated assuming there was no overlap between these cases; i.e. technical success was achieved in 1072 (1258 – 132 - 54) lesions.

Table 4. Sample Size – Primary Safety Endpoint

Primary Safety Endpoint	
Performance goal	80%
Anticipated freedom from MAE	91%
Significance level	.025
Statistical test	One-sided exact binomial test
Desired power level	90%
Required sample size prior to 10% 30-day attrition rate	110
Required sample size after attrition adjustment	121

Table 5. Sample Size – Primary Effectiveness Endpoint

Primary Effectiveness Endpoint	
Performance Goal	76%
Anticipated technical success rate	86%
Significance level	.025
Statistical test	One-sided exact binomial test
Desired power level	90%
Required sample size (target lesions)	165
Estimated subjects required for required number target lesions*	110

* Assumes 1.5 target lesions treated per subject; a ratio calculated from the studies in the atherectomy literature review

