8.8. Withdrawals and Loss to Follow-up

Participation is completely voluntary and each subject is free to withdraw from the study at any time. An investigator also has the right to withdraw the subject from the study in the event of reasons concerning the health or well-being of the subject, or in the case of lack of cooperation. Should a subject decide to withdraw for any reason, or should the investigator decide to withdraw the subject, all efforts will be made to complete and report the observations up to the time of withdrawal as thoroughly as possible. A complete final evaluation at the time of the subject's withdrawal must be made and an explanation given of why the subject is withdrawing or being withdrawn from the study.

The reason for and date of withdrawal must be recorded on the subject's End of Study CRF. If the reason for the withdrawal is a device-related or procedure related AE, the event must be reported to the Sponsor and recorded in the CRF.

If the procedure is aborted, the subject does not need to complete the follow-up assessments, unless the subject is converted to surgical repair. The subject's enrollment roster position may not be made available to other subjects.

If a subject dies during the course of the study, the Sponsor will request an autopsy provided the subject authorized an autopsy in the event of death during the course of the study. Autopsy observations should include documentation of condition of body organs and determination of device and/or procedure relationship to death.

All efforts will be made to retain subjects in order to collect data at all the follow-up visits (30 days, 6 months). Due diligence in reaching the subject must be made by:

- Two documented telephone contact attempts, emails, or regular postal mail letters; and
- Certified letter

After the above attempts were made, if no response is obtained, the final evaluation of a given subject will be the last visit at which study-related procedures were performed on that subject. The End of Study CRF page will need to be completed and communication attempts will need to be documented.

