5. ENDPOINT ALGORITHMS

5.1 Safety Endpoints

For missing values, an adjustment to the denominator will be made based on the amount of evaluable data for safety-endpoints.

Safety denominator adjustment: For each visit (or reporting time point), the event rate will be calculated as the number of subjects with certain event term over the number of evaluable subjects. The evaluable subjects at each reporting time point include all subjects who are enrolled by the snapshot date and

- 1) Had an event within (on or before) the reporting cutoff days, or
- 2) Had a follow-up at or after the lower limit of the reporting window, or
- 3) The withdrawal consent date/recorded lost-to-follow-up date at or after the lower limit of the reporting window

‘Days to event’ (date of earliest event – date of index procedure) and ‘Days to last contact’ (date of last contact – date of index procedure) are usually used for the determination of the eligibility of the ‘evaluable subject’. The last contact date will be calculated based on the information gathered from all available dates during the follow-ups.

The ‘Reporting Cutoff Days’, ‘Lower limit of the Reporting Window’ and the correspondent visits are as the following:

Visit	Reporting Cutoff Days	Lower Limit of the Reporting Window (days post-index procedure)
1-month	30 days post-index procedure	Days to last contact: 23
6-month	180 days post-index procedure	Days to last contact: 166

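### Protocol 8.8 lets one unanswered round of contact close a subject with 30-day MAE status unknown, and SAP 5.1 may then count that subject as event-free

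*Protocol*

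**What the plan says.** Protocol 8.8 opens with a general aim: "All efforts will be made to retain subjects in order to collect data at all the follow-up visits (30 days, 6 months". The required effort is then "Two documented telephone contact attempts, emails, or regular postal mail letters; and" a certified letter. After that, "if no response is obtained, the final evaluation of a given subject will be the last visit at which study-related procedures were performed". The closing step is administrative: "The End of Study CRF page will need to be completed and communication attempts will need to be documented". The paragraph does not say which visit it applies to, whether the attempts are repeated at the next visit, or whether vital status is to be sought elsewhere.

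SAP 5.1 defines who is evaluable for safety at a time point. Route 1 is an event by the cutoff day. Route 2 is "Had a follow-up at or after the lower limit of the reporting window", with no upper limit. Route 3 is "The withdrawal consent date/recorded lost-to-follow-up date at or after the lower limit of the reporting window". For the 1-month visit the lower limit is given as "Days to last contact: 23". The event rate is subjects with the event divided by evaluable subjects.

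SAP 4.7 describes the same denominator differently. It takes subjects who had a component event or whose follow-up reached the lower limit, and it does not mention the loss-date route. The imputation and tipping-point analysis described there concern missing effectiveness measurements. For safety, only the denominator is adjusted.

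Protocol 7.9 plans for loss: "Assuming 10% attrition over 30 days, initial enrollment of 121 subjects is necessary".

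**The concern.** Read together, these sections allow a subject who does not answer around day 30 to leave the study with nobody knowing whether death, amputation, re-treatment or another MAE component occurred by day 30. SAP 5.1 route 2 would accept a contact months later as settling that status, yet 8.8 does not ask for one. All-cause death is a component and could be checked without a visit, and 8.8 does not ask for that either.

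What happens next depends on the recorded loss date. If it is day 23 or later, route 3 puts the subject in the denominator. With no known event, the subject adds nothing to the numerator of the MAE rate and so counts as event-free. If it is earlier, the subject is dropped. In both cases the 6-month data are lost.

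Subjects who cannot be reached may be in hospital elsewhere or dead, so the loss need not be random. In a single-arm test against a fixed 80% goal, both routes can favour the device. Freedom from 30-day MAE is one of the two endpoints that must succeed.

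**Working it through.** **Inputs.** Safety goal 80%, anticipated freedom from MAE 91%, 90% power, 110 evaluable, 10% attrition, 121 enrolled (Protocol 7.9). One-sided exact binomial at 0.025 (Protocol 7.2 and 7.9). Lower limit day 23 (SAP 5.1).

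**1. The plan's own figure.** Normal approximation: n = [1.960 × √(0.80 × 0.20) + 1.282 × √(0.91 × 0.09)]² / 0.11² = 109.4, so 110. The exact test at n = 110 needs at least 97 event-free and has 88.2% power. The attrition step is 110 × 1.10 = 121. The plan's 110 and 121 are therefore reproduced to within a small tolerance. Under the planned loss, 121 × 0.90 = 108.9, about 109 seen and 12 not seen.

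**2. Pass marks of the exact test.** With n = 109, at least 96 event-free are needed (at most 13 MAE; type I error 1.9%). With n = 121, at least 106 are needed (at most 15 MAE; type I error 2.0%).

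**3. Unseen subjects dropped (loss date before day 23).** If the 12 have the same MAE rate as the rest, type I error stays at 1.9%. Bias arises only if their rate is higher. A trial that just passes at 109 with 13 events would fail at 121 if 3 or more of the 12 had an MAE, since 13 + 3 = 16 exceeds 15.

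**4. Unseen subjects counted event-free (loss date on or after day 23).** Let u be the number unseen. The n = 121 rule then needs only 106 − u event-free among the 121 − u observed. Type I error is P(X ≥ 106 − u), with X binomial (121 − u, 0.80). This assumes that unseen subjects have the same true MAE rate and that none of their events is captured.

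| Unseen u | Observed | Needed among observed | Type I error at a true 80% |
|---|---|---|---|
| 0 | 121 | 106 | 2.0% |
| 3 | 118 | 103 | 2.7% |
| 6 | 115 | 100 | 3.5% |
| 9 | 112 | 97 | 4.7% |
| 12 | 109 | 94 | 6.1% |

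Here the bias needs no informative loss. At a true 80%, the expected estimate with 12 unseen is (109 × 0.80 + 12) / 121 = 99.2 / 121 = 82.0%.

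**5. Power if unseen subjects were dropped and later recovered, at 91% freedom from MAE.** n = 109: 88.8%; n = 112: 86.9%; n = 115: 90.7%; n = 118: 89.1%; n = 121: 92.3%. Exact power is saw-toothed, so recovering 3 subjects lowers it and recovering 9 leaves it almost unchanged.

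**The case against.** The strongest reply is that 8.8 does not forbid later contact. Its opening aim names both visits, and the paragraph does not say that one missed visit triggers closure or when the End of Study form is completed. Other sections treat a missed visit as something short of leaving the study: Protocol 9.3 classes departures from the follow-up schedule as deviations, and SAP 5.24 has rules for a scheduled visit that was not done. This stands to the extent that a reader might infer that subjects missed at 1 month will never be sought again, and the text does not go that far. But a final evaluation plus an End of Study form is what sites will act on, and nothing after it calls for a new attempt.

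Second, deaths are partly covered. Protocol 10.1 and 10.2 require any death to be reported, and SAP 5.1 counts any known event by the cutoff, whatever the follow-up. That holds only if the site learns of the event.

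Third, not all of the planned 10% can be recovered by calling. Section 8.8 also covers withdrawal by the subject or investigator, and aborted procedures that are excused from follow-up. No document says how many losses would come from non-response. This stands, and it makes 12 an illustrative upper figure for the planned loss.

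Finally, the route-3 reading is not certain. The lower limit is expressed in days to last contact, and SAP 4.7 speaks only of follow-up, so an analyst could exclude a subject with only a loss date. That is a reason to reconcile the two sections.

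**Conclusion.** The point holds and should be addressed. As written, 8.8 permits closure after one unanswered round of contact with 30-day MAE status unknown, although a later contact would be usable under the SAP.

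A reader might infer that such a subject becomes permanently missing for the primary safety endpoint. The documents do not support that as a general statement. Contact attempts made around day 30 would normally give a loss date after day 23, and route 3 then makes the subject evaluable. The more likely problem is an unobserved success.

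A reader might also infer that recovering subjects would raise power. The range of 88.8% to 92.3% is a ceiling that assumes every planned loss is recoverable, and partial recovery can lower power. The case therefore rests on bias.

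The size is illustrative: type I error of 3.5% with 6 unseen and 6.1% with 12, against 2.0% with full data. These figures depend on the same MAE rate in unseen subjects, none of their events captured, and route 3 applied as written. The actual number of such subjects cannot be known from the documents.

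**What to change.** In Protocol 8.8:
- Treat non-response at 1 month as a missed visit.
- Complete the End of Study form for loss to follow-up only after the same attempts have also failed in the 6-month window.
- At any later contact, record the status of each MAE component through day 30.
- Before closing a subject, check vital status through the treating physician, the medical record or public records, where consent allows.

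In the SAP, reconcile 4.7 with route 3 of 5.1 so that a loss date alone does not make an unseen subject event-free.

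The cost is a short edit to each document and a few more calls and record checks, for about 12 subjects at most under the planned attrition. It needs no extra visits or enrolment. The downside for the sponsor is that recovered subjects may add events.

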9. STUDY MANAGEMENT CONSIDERATIONS

9.1. Data Management: Collection of Clinical Data

The Sponsor and/or assigned designee will be responsible for the processing and quality control of the data. Source data for safety will be retained for at least 2 years after the termination/completion of the study or after the approval/withdrawal of the marketing application, whichever occurs later. All other source data, source documents, CRFs, copies of protocols and protocol amendments, device accountability forms, correspondence, subject identification lists, informed consent forms, and other essential documents must also be retained for a period of at least 2 years as detailed above. Rex Medical, L.P. will inform the investigator/institution when these documents are no longer required to be retained.

No study document or image will be destroyed without prior written agreement between the Sponsor and the Investigator. Should the Investigator wish to assign the study records to another party or move them to another location, advance written notice must be given to the Sponsor.

9.2. Protocol Modifications

No changes from the final approved (signed) protocol will be initiated without the IRB's prior written approval or favorable opinion of a written amendment, except when necessary to eliminate immediate hazards to the subjects or when the change involves only logistics or administration. The Principal Investigator will acknowledge the amendment by signing the Protocol Agreement.

9.3. Protocol Deviations

A protocol deviation is the non-adherence to or divergence from the protocol-specific study procedures. For example, violations of the inclusion and exclusion criteria, deviations from the schedule of required follow-up assessments, improper or lack of consent, and lack of IRB approval, would all be considered protocol deviations. A protocol deviation undertaken to protect the life or physical well-being of the patient in an emergency is a special circumstance that must be reported to the Sponsor and the reviewing IRB within 5 working days. The Sponsor must report the deviation to the FDA within 5 working days after the Sponsor learns of the deviation. No other type of prospective protocol deviation is permitted without prior approval. A record of all protocol deviations will be maintained and reviewed throughout the conduct of the study. The Sponsor will address deviations and take appropriate corresponding action. Continued non-compliance with the study protocol may lead to termination of the Investigator's participation in the study.

Subject eligibility for the study is determined by site-measured anatomic criteria; not by core laboratory values. For this reason, enrollment of subjects with core laboratory-determined anatomic measurements on the baseline, pre-interventional angiogram will not be protocol deviations.

9.4. Information to Study Personnel

The Investigator is responsible for giving information about the study to all staff members involved in the study or in any element of subject management, both before starting the study procedures and during the course of the study (e.g., when new staff become involved). The Investigator must ensure that all study staff members are qualified by education, experience, and training to perform their specific responsibilities.

The monitor is responsible for explaining the protocol to all study staff, including the Investigator, and for ensuring their compliance with the protocol throughout the study. Additional information will be made available during the study when new staff become involved in the study, and as otherwise agreed upon with either the Investigator or the monitor.

10. ASSESSMENTS OF SAFETY

10.1. Defining Adverse Events

An adverse event is an untoward medical occurrence or exacerbation of an existing medical condition subsequent to the experimental therapy. Adverse events are rated in several ways:

- Severity (mild, moderate, severe)
 - **Mild:** No limitation of usual activities, no therapy or only symptomatic therapy required to treat the injury or illness.
 - **Moderate:** Some limitation of usual activities or specific therapy is required.
 - **Severe:** Inability to carry out usual activities, hospitalization, emergency treatment, life threatening events, or death.

- Anticipated (anticipated, not anticipated)
- Device and procedure relationships (unrelated, possibly related, definitely related, or relationship unknown)
 - **Unrelated:** The clinical event is completely independent of study procedure/study device and/or evidence exists that the event is definitely related to another etiology.
 - **Possibly related:** The clinical event occurs within a reasonable time sequence to study procedure/study device and there is some evidence to “possibly” suggest a causal relationship. However, the influence of other factors such as underlying disease, concomitant medications, or concurrent treatment may have contributed to the event.
 - **Definitely related:** The clinical event occurs in a plausible time relationship to study procedure/study device and cannot be explained by any concurrent disease or other devices, drugs or chemicals.
 - **Relationship unknown:** The relationship to the study procedure/study device is not known.

Adverse events will be categorized as either serious or non-serious. A Serious Adverse Event (SAE) is an event that meets at least one of the following:

- Is fatal
- Is life-threatening
- Results in persistent or significant disability/incapacity
- Results in permanent impairment of a body function or permanent damage to a body structure
- Results in hospitalization or prolongs a hospitalization
- Necessitates medical or surgical intervention to preclude permanent impairment of a body function or permanent damage to a body structure

An MAE is a subcategory of adverse events that include any of the primary safety endpoints occurring within 30 days of the index procedure. An adverse device effect (ADE) is any unwanted and unintended response to a medical device. This definition includes any event resulting from insufficiencies or inadequacies in the instructions for use or the deployment of the device and any event that is a result of user error. A serious adverse device effect (SADE) is an adverse device effect that has resulted in any of the consequences characteristic of a serious adverse event or that might have led to any of the consequences if suitable action had not been taken or intervention had not been made or if circumstances had been less opportune. An unanticipated adverse device effect (UADE) is defined as “any serious adverse effect on health or safety or any life-threatening problem or death caused by, or associated with, a device, if that effect, problem, or death was not previously identified in nature, severity, or degree of incidence in the investigational plan or application (including a supplementary

application), or any other unanticipated serious problem associated with the device that relates to the rights, safety, or welfare of subjects.”

Section 15.1 (page 44, below) includes a list of possible adverse events associated with endovascular repair, including those events considered major device-related events and major morbidity. These events are considered reportable at all time points throughout the trial and require submission to the Sponsor.

Events not captured in these two categories are not considered in the primary effectiveness or primary safety analyses, regardless if they are device-related or serious. These events must nonetheless be documented on the Adverse Event CRFs. Additionally, any event with an outcome of death must be reported.

10.2. Reporting of Adverse Events

In addition to events considered in the primary effectiveness and primary safety analyses, all device- and/or procedure-related adverse events, as well as events resulting in death, must be captured on the Adverse Event Case Report Form. The report should include, wherever possible, severity, duration, outcome, and the Investigator’s written medical judgment as to the relationship of the adverse event to the study device, procedure, or underlying disease (i.e., not related, possibly related, definitely related, or relationship unknown).

All SAEs must be reported to the Sponsor or its Contract Research Organization (CRO) within 5 business days of the Investigator’s knowledge of the event. The event is reported in the electronic data capture system. IRB notification of the adverse event may also be required, depending on the conditions of approval or requirements of the respective committee. Any unanticipated adverse device effects must be reported to the Sponsor/CRO within 1 working day from when the Investigator first learns of it.

Non-serious reportable adverse events are to be submitted via the electronic data capture system in a timely fashion. Certain reportable events may require adjudication; therefore, supporting documentation must be sent to the Sponsor/CRO.

11. DEVICE ACCOUNTABILITY

11.1. Accountability and Procedures

- a.) Each device shipment must be documented on the Device Accountability Log and include the receipt, dispensing, and return of investigational devices.
- b.) When a shipment is received, the Investigator (or designee) must record on the Device Accountability Log the date received and the Catalog and Lot Number of each device. It is recommended that the Packing List also be signed and dated.
- c.) Investigational devices must be kept in a secure, limited access storage area under recommended storage conditions (room temperature).

- d.) During the course of the study, the following information must also be noted on the Device Accountability Log:
 - Identification number of the subject for whom the device was intended
 - Procedure date
- e.) The Device Accountability Log must be readily available for inspection by representatives from the Sponsor, the IRB, and/or other relevant regulatory authorities at any time.
- f.) The Device Accountability Log and device storage locations will be reviewed during monitoring visits.
- g.) All unused investigational devices must be returned to Rex Medical L.P. once it is determined they will not be used. Upon completion of the study, all unused investigational devices must be returned to Rex Medical L.P., if any remain at the site. The monitor is to verify return.

